accordingly. We expect that the data analysis will consist of regression analysis of the temporal pain level distribution between the group with and without the SHGNB. Continuous variable data, with normal distributions, subgroup analysis of the secondary objectives will be compared using a Student's t- test.

▪ **Sample size calculation**

Sample size calculations are based on published data showing the average pain felt by ladies post uterine artery embolization being of 7/10 with a standard deviation of approximately 2.5. The published study of SHGNB for UAE demonstrated a decrease in pain from 7 to 5-2 depending on the analgesics regimen used [6]. We opted for the conservative drop in pain scale from 7 to 5 with a standard deviation of 2.5. This gives an effect size of 0.8. With type I error (alpha) set at 0.05 and type II error (beta) set at 0.2 (power of 80%), the sample size calculations yields a needed sample size of 42. We expect up to a 20% drop out rate due to loss to follow-up, giving a total sample size needed of 50, leaving 25 patients per group. [8]

If the analysis of the data after recruiting 50 patients is highly suggestive of an effect but without statistical significance, and if the calculations suggest we could get statistical significance by doubling the number of participants, and there have been no significant adverse events from the nerve block, we would increase the number of patients to 100. If adverse events have occurred, the number would not be increased unless approval by the ethics committee.

▪ **Interim analysis**

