Subject data collection at the time of enrollment will include demographics, relevant medical history and vital signs. Subjects will be followed-up as outlined in Table 1 to assess adverse events related to the procedures and clinical success of the procedure. Individual data collection will be considered complete at the time of the follow-up consultation 4-6 months after the UAE procedure.

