7.2. Consent

In this study we would be obtaining written informed consent from all patients. This will be obtained at the time of the first consultation or on the day of the procedure if the patient has had time to read the information package and agrees to it. The consent will be signed outside of the angiography suite and the consent will be obtained by an interventional radiologist at the time of the consultation who will not be involved in the procedure itself. The consent for the embolization will be separate than that for the hypogastric nerve block research project itself.

Table 1: Schedule of Study Procedures

Parameter	Consult up to 3m prior to procedure	Day of the procedure	Time between procedure and follow-up consult	Follow-up consult 4-6 m after procedure
Information package	X			
Informed consent signed	X	or X		
History& exam	X	X		X
Randomization		X		
UAE/block		X		
Recovery with data gathering of time in hospital		X		
Visual pain scale sheets give to patient		X		
Results from visual pain scale sheets gathered from patient			X	or X

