7.5. First 10 days following the procedure

The patient has some pain scoring sheets to fill (3/d for the first three days and the 1/d until day 10 post procedure) which record the amount of pain and the amounts of pain medications used. She can fill them on hard copies provided to her and bring them back at the time of the consult or mail them to us in a prestamped envelope. She can also use a internet anonymous filing system to fill out the forms.

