7.6. Follow-up Consult

The patient will be seen in follow-up consult 4-6 months after the procedure as per routine protocol. At that time, the patient is evaluated for successful treatment and for possible delayed complications of the UAE. Also a final questionnaire will be filled out regarding any issues that could have arisen from the SHGNB.

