Appendix IV - Sheets to be filled out by patient

We encourage you to fill out these sheets via the internet if possible using the following anonymous login name and password to sign in. Otherwise you can use these hard copies and mail them back to us in the prestamped envelope or bring them back to your follow-up visit in 4-6 months.

You will receive an email giving you a link to the internet forms

Your anonymous login name for the internet is: _____

Your Password is: _____

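### Apart from pain and analgesic use, no adverse-event, emergency-visit or readmission question is scheduled between discharge and the 4-6 month consult, and the 50-patient extension rule sets no safety data cut

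*Combined protocol and SAP*

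**What the plan says.** Section 7.1 makes Table 1 the schedule for safety follow-up: "Subjects will be followed-up as outlined in Table 1 to assess adverse events related to the procedures and clinical success of the procedure". Table 1 (under section 7.2) has no row for adverse events. In its column between the procedure and the follow-up consult, the only row marked is "Results from visual pain scale sheets gathered from patient", and that row may instead be met at the consult itself.

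Section 7.5 describes the home sheets as ones "which record the amount of pain and the amounts of pain medications used". The synopsis (Study Design & Procedure) likewise limits home data to the visual analogue scale and self-recorded medication. Appendix IV lets patients "mail them back to us in the prestamped envelope or bring them back to your follow-up visit in 4-6 months".

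Harms are recorded during the procedure (Appendix II) and in recovery (Appendix III). They are next asked about at 4-6 months. Section 7.6 says "At that time, the patient is evaluated for successful treatment and for possible delayed complications of the UAE" and "Also a final questionnaire will be filled out regarding any issues that could have arisen from the SHGNB", and Appendix V lists complications since the embolization.

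Section 5 (Sample size calculation) allows expansion to 100 patients, among other conditions, when there have been no significant adverse events from the block. The trigger reads "If the analysis of the data after recruiting 50 patients is highly suggestive of an effect". No follow-up requirement is attached to it.

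**The concern.** Section 1.3 puts discharge orders at 4-5 hours after the procedure. The block harms named in the synopsis (Safety) include infection, bowel injury, bleeding and nerve injury, and these can declare themselves after the patient has gone home. Section 3 makes adverse events, pain- or complication-related admissions and emergency return visits for pain secondary objectives, and the synopsis rationale gives fewer return visits as one aim of better pain control.

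If such events are first asked about 4-6 months later, some will be forgotten or misdated. An event never elicited is then tabulated as no event, which can hide a difference between arms.

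The extension rule has a related weakness. It turns on an absence of events, and nothing in it separates a patient who was asked and had none from a patient who has not yet been asked.

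**Working it through.** **1. Collection points, side by side**

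| Period | What is scheduled | Source |
|---|---|---|
| Procedure | Immediate complications of embolization and of block or sham | Appendix II |
| Recovery | Complications; admission yes/no | Appendix III |
| Home, to day 10 | Pain and pain medication | Synopsis, 7.5 |
| Day 10 to consult | Nothing beyond return of the sheets | Table 1 |
| 4-6 months | History and exam, complications, block questionnaire | Table 1, 7.6, Appendix V |

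The item fields of the Appendix IV sheets are not visible in the text available, so their content is taken from the synopsis and section 7.5.

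**2. Data cut for the two looks.** The interim look (section 5) is set at 20 patients who have completed the study, and section 7.1 defines individual completion as the 4-6 month consult. The extension decision is tied to recruitment of 50. The plan therefore attaches a follow-up requirement to one look and none to the other.

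**3. The plan's 50.** Effect size 2/2.5 = 0.8. A one-sided two-sample t-test at alpha 0.05 and 80% power needs 21 per arm, or 42. Adding 20% gives 42 x 1.2 = 50.4, about 50, or 25 per arm. The figure is used here only as the size of the gate.

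**4. Patients not yet at the consult.** The documents give no accrual rate, so a range is assumed. If the decision is taken at the 50th procedure, the number pending is monthly accrual x 4 to 6 months:
- 1 per month: 4-6 of 50 (8-12%)
- 2 per month: 8-12 (16-24%)
- 4 per month: 16-24 (32-48%)

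If the decision waits for every consult, the number is 0.

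**5. What the gate can see.** The synopsis puts significant block complications below 0.5%. P(no event in n block patients) = (1 - p)^n. The case n = 13 is the extreme one: 24 of 50 pending, so 26 asked, half of them block patients. It assumes that an unasked patient contributes nothing.
- p = 0.5%: 0.995^25 = 0.88; 0.995^13 = 0.94
- p = 2% (illustrative, above the plan's estimate): 0.98^25 = 0.60; 0.98^13 = 0.77

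With zero events seen, the one-sided 95% upper limit is 1 - 0.05^(1/n): 11.3% for n = 25 and 20.6% for n = 13.

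**The case against.** The strongest reply is that the plan is not silent on safety after discharge. Pain is itself a listed adverse event of both block and embolization, and it is scored at home for up to 10 days. The online survey is partly meant to flag significant pain (section 1.3). Known procedure-related events are followed to resolution, a medical monitor reviews serious events, data are reviewed routinely, and there is a safety committee. This stands to the extent that a reader might infer that no adverse event at all is asked about at home; the documents do not support that. It does not close the gap for other harms, because these provisions act on pain or on events already reported and none schedules a question to the patient.

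A reader might also infer that the 50-patient decision will be taken before recent patients have been asked. The text does not say so. It sets no data cut, and waiting for complete data is an open reading. What stands is that an early decision is permitted.

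Third, "We expect up to a 20% drop out rate due to loss to follow-up" might be read as 0.2 x 25 = 5 block patients with no post-discharge safety data. The figure is a ceiling used for sample size, and a patient who misses the consult may still have returned sheets or reported an event.

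Finally, an assumed event rate of several percent would make the gate's timing look decisive. The plan expects under 0.5%, and at that rate the gate is insensitive whatever its timing.

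**Conclusion.** The point holds in a limited form. As written, the plan schedules no inquiry about non-pain adverse events, emergency visits or readmissions between discharge and 4-6 months, so the promise in section 7.1 is not met by Table 1, and several secondary outcomes depend on spontaneous report or late recall. The conclusion about the sheets rests on their description, since the fields themselves cannot be seen.

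The extension rule lacks a safety data cut. At an assumed 1-4 patients per month, between 4 and 24 of 50 patients could be pending if the decision were taken at the 50th procedure. The effect on the gate is modest at the plan's own rate: the chance of seeing no event moves from about 88% to at most about 94%. The main reason to act is therefore the quality of the secondary outcomes; a defined data cut for the gate is the smaller gain. The change is worth making before recruitment proceeds, but it does not touch the primary pain comparison.

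**What to change.** 1. Add a short dated tick-list to the existing home sheets, paper and online, at day 3 and day 10: fever; new abdominal, back or leg symptoms; bleeding; emergency visit; hospital admission.
2. Add an adverse-event row to Table 1 that covers the interval between procedure and consult.
3. Ask that paper sheets be mailed in the prestamped envelope after day 10, and not held until the consult. Without this, day-10 answers on paper could arrive no earlier than the consult does.
4. In section 5, state that the 50-patient decision uses adverse-event data through at least day 10 for all patients who returned sheets. Report with it how many patients have no post-discharge data and how many have not reached the 4-6 month consult.

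The cost is slightly longer home entries on two days, a few sentences of protocol text, and a short wait for sheets to come back before the decision. No treatment or visit changes.

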7.2. Consent

In this study we would be obtaining written informed consent from all patients. This will be obtained at the time of the first consultation or on the day of the procedure if the patient has had time to read the information package and agrees to it. The consent will be signed outside of the angiography suite and the consent will be obtained by an interventional radiologist at the time of the consultation who will not be involved in the procedure itself. The consent for the embolization will be separate than that for the hypogastric nerve block research project itself.

Table 1: Schedule of Study Procedures

Parameter	Consult up to 3m prior to procedure	Day of the procedure	Time between procedure and follow-up consult	Follow-up consult 4-6 m after procedure
Information package	X			
Informed consent signed	X	or X		
History& exam	X	X		X
Randomization		X		
UAE/block		X		
Recovery with data gathering of time in hospital		X		
Visual pain scale sheets give to patient		X		
Results from visual pain scale sheets gathered from patient			X	or X

7.3. Visit on day of Consult

The following should be done at the initial visit:

- Obtain consent for the uterine fibroid embolization procedure
- Review protocol specific inclusion and exclusion criteria.
- Assess whether patient is able to provide consent or not. If the patient is appropriate for the study, informed consent is obtained. This consent will be obtained by an interventional radiologist who will not be involved in the procedure itself.
- Obtain relevant medical history and current demographic data.

Presence of inclusion criteria and absence of exclusion criteria will be verified on the designated source documents and eCRF.

7.4 Day of the UAE procedure

If consent had not been obtained at the day of the consult because the patient wanted to think about it some more, the patient could be asked at this time whether they want to participate in the study or not. If this is the case, all discussion will occur outside of the angiography room and the patient given information sheet and will be given time to decide whether they would like to participate or not.

If they have decided to participate, a pre-randomized envelope will be opened and will decide whether the patient gets the hypogastric block or the sham procedure. UAE will proceed as per usual. The patient will be recovered for at least 4 hours in the recovery room. Data regarding pain management while in the recovery room will be gathered on the provided information sheets (see appendix). Before discharge, the patient will be seen by one of the interventional radiologists to complete a visual analog pain scale and collect the information that has been gathered. The patient will be provided an anonymization number and reminded to fill out the pain forms at home via hard copy that

she can bring back to us at the time of the follow-up or mail to us (see appendix), or that she can fill out anonymously by internet.

Procedural information will be collected and stored in a secure area for future analysis.

7.5. First 10 days following the procedure

The patient has some pain scoring sheets to fill (3/d for the first three days and the 1/d until day 10 post procedure) which record the amount of pain and the amounts of pain medications used. She can fill them on hard copies provided to her and bring them back at the time of the consult or mail them to us in a prestamped envelope. She can also use a internet anonymous filing system to fill out the forms.

7.6. Follow-up Consult

The patient will be seen in follow-up consult 4-6 months after the procedure as per routine protocol. At that time, the patient is evaluated for successful treatment and for possible delayed complications of the UAE. Also a final questionnaire will be filled out regarding any issues that could have arisen from the SHGNB.

7.7 Protocol Revisions and/or Deviations

With the exception of emergency situations, no changes or deviations in the conduct of this protocol will be permitted.

The Research Ethics Board (REB) that granted original approval for the study must be notified of all changes in the protocol, and must provide documented approval of any change or deviations that may increase risk to the subject, and/or that may adversely affect the rights of the subject or validity of the investigation.

In the event of an emergency, the investigator will institute any medical procedures deemed appropriate. However, all such procedures must be promptly recorded and reported to the REB.

7.8. Data Collection:

Patient data will be reviewed by the research investigator on a routine basis to ensure any adverse events and information gathered were correctly recorded. The following datasheets will be used through-out the study:

1. **Screening Form (appendix 1)** will be completed by the enrolling radiologist and will include demographic data and inclusion and exclusion criteria.
2. **Data sheet at time of UAE (appendix 2)** will be completed by the treating interventional radiologist.
3. **Data sheet at time of discharge from recovery room (appendix 3)** will be completed by the treating interventional radiologist.
4. **Data sheets during the following 10 days post procedure (appendix 4)** will be completed by the patient

5. **Data sheet at time of follow-up consult (appendix 5)** will be completed by the interventional radiologist and the patient
6. **Data sheet regarding symptoms and changes in quality of life caused by the fibroids UFS-QoL questionnaire (appendix 6)** will be completed by the patient at the time of the first and last consultation.

No unique patient identifying information will appear on the screening form that will be coded only by a study identification number. A key linking the patient name and study identification number will be maintained in a separate database. All datasheets will be kept in a locked, dedicated research office. All computer records will be maintained in a password-protected, limited access folder. Paper records will be maintained in a locked, dedicated research office. All patients' charts will be kept in secure storage for 25 years, as required by legislation. All privacy regulations will be respected. Only the research coordinator, principal investigator, and the safety committee will have access to the patient data.

Data integrity will be maintained throughout the study. Logic rules within the database will be used to maximize integrity, and random data validation checks will be performed routinely. The research investigator will review studies and patients' data on a monthly basis to ensure that patient follow-up is proceeding as expected. All cases where the research investigator finds a discrepancy in imaging interpretation or outcome assessment will be reviewed by the Adjudication Committee, consisting of the principal investigators. An independent radiologist from the MUHC will be asked to determine the outcome of a dispute amongst the Adjudication Committee.

8. Data Analysis:

Data will be collected and tabulated using the commercially available JMP10/SAS statistical analysis software (SAS Institute Inc., Cary, NC, USA). Descriptive statistics will be provided for the efficacy outcome results and will be presented in terms of percentage, frequency, means and 95% confidence interval of the means. Differences between both groups will be compared using the Chi-square test for categorical variables and Student's t- test for the continuous variables. ANOVA test and multivariate logistic-regression analysis will be used to compare interplay of more than two variables. Two-tailed p-values of less than 0.05 will be set for statistical significance.

9. Ethical considerations:

Research Ethics approval from the MUHC Research Ethics Board office will be obtained prior to the commencement of the study or related research procedures. All patients will be informed about the data that will be gathered for the study. All patients will have the ability to refuse participating in the study as soon as they are able to evaluate it and give their approval or not. Patients will always be given options to ask questions at any time and questions will be answered in a non-intimidating way so as to try to avoid influencing the patient's decision. At any time, the patient can decide to remove himself from the study. If this is the case, he will receive the standard of care.

No unique patient identifying data will appear on the sheets that will be coded only by study identification number. A key linking the patient name and study identification number will be maintained in a separate database. All datasheets will be kept in a locked, dedicated research office. All computer records will be maintained in a

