The UFE procedure has been found to be safe and effective with fewer complications than total hysterectomy. Approximately 80-90% of women get clinical improvement after uterine artery embolization and 97% would recommend the procedure to others [4]. The most common complication which is almost universal, is that of pain post embolization.

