Because of the success of the group in Ottawa in performing the SHGNB, we have just recently started to offer this procedure as well. Initial results are also very encouraging with recovery nurses informing us that in general the patients seem to be doing much better with the nerve block in place. However the data remains anecdotal. There have been no studies to date comparing simple oral/IV sedation to SHGNB + oral/IV sedation. For this reason, probably, the procedure has been very slow to be adopted by people who perform UAEs. We believe that, to put this issue to rest, there is a necessity for such a comparative trial and, especially important in the context of a subjective outcome such as pain, it is our belief that a randomized double-blinded control trial is needed to obtain conclusive data. This was the reason this study was put together.

2. Research Question:

Is there a difference in subjective pain score patients experience and in the need for analgesics post uterine artery embolization for fibroids if the patients undergo a superior hypogastric nerve block during the embolization procedure.

3. Objectives:

The primary objective is to assess:

- Reduction in subjective pain as measured by patient self administration of visual analogue scale and reduction in use of oral analgesics at home and IV/oral analgesics while in hospital

The secondary objectives are:

- Differences in adverse events between groups with and without SHGNB
- Differences in pain/complication related admissions between groups with and without SHGNB
- Differences in pain in relation to total volume of fibroids between groups with and without SHGNB
- Differences in pain in relation to fibroids vs. adenomyosis between groups with and without SHGNB
- Differences in successful outcome of the embolization both by imaging and clinically between groups with and without SHGNB
- Differences in admission rates
- Differences in rates of return visits to ER for pain issues
- Patient use and appreciation of the online pain survey

4. Implications:

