Appendix V - At follow-up consult

Post UAE MRI review:

of fibroids (1/2/3/>3): _____

Size of three largest fibroid labeled on pre UAE consult

1) _____ x _____ x _____ (cm) % necrosis: _____

2) _____ x _____ x _____ (cm) % necrosis: _____

3) _____ x _____ x _____ (cm) % necrosis: _____

% necrosis overall: _____

Adenomyosis No Yes: Focal Diffuse

% necrosis of adenomyosis: _____

Ovarian anastamosis: No
 Left
 Right

Complications since the UAE:

Persistent Pain - Where: _____

Arrested periods - Since when: _____

Vaginal bleeding outside of periods

Symptoms of peri-menopause (hot flushes, nights sweats, etc)

Since when: _____

Endometritis - treated when: _____

Other infection – where: _____ treated when: _____

Need for surgery - When: _____

Why: _____

Continued symptoms as they were before the UAE (no clinical improvement)

Other: _____

Clinical outcome of UAE:

- Complete resolution of symptoms
- >80% improvement in symptoms
- 50-80% improvement in symptoms
- 20-50% improvement in symptoms
- <20% improvement in symptoms

Is patient happy with the outcome (scale 0-10): _____

Attach Patient's UFS-QOL questionnaire

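### The five-level symptom-relief item is ordered, but the only test named for categorical data ignores order; naming an ordinal analysis is a cheap gain for a secondary outcome

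*Combined protocol and SAP*

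**What the plan says.** - **The item.** The follow-up form in Appendix V rates clinical outcome on five levels, running from "Complete resolution of symptoms" through more than 80%, "50-80% improvement in symptoms" and 20-50%, down to less than 20% improvement. The order is built into the labels.
- **Its role.** Section 3 lists as a secondary objective "Differences in successful outcome of the embolization both by imaging and clinically between groups with and without SHGNB". The synopsis has the same objective. Neither defines clinical success.
- **The test.** Section 8 states "Differences between both groups will be compared using the Chi-square test for categorical variables", with Student's t-test for continuous variables. The synopsis also names chi-square for categorical variables.
- **Other methods.** "ANOVA test and multivariate logistic-regression analysis will be used to compare interplay of more than two variables". That sentence does not cover a plain two-arm comparison of one item. Section 5 allows the analysis to be adapted after a check of the data distribution, but the context is normality of continuous data.
- **Significance level.** "Two-tailed p-values of less than 0.05 will be set for statistical significance".
- **Expected results.** Section 1.2 gives one figure: "Approximately 80-90% of women get clinical improvement". It does not define improvement or spread it over the five levels. Section 5 sizes the trial on pain only.

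**The concern.** A Pearson chi-square on a 2x5 table asks whether the arms differ in any way at all. It would give the same p-value if the five labels were shuffled. The question here has a direction: do women in one arm end up with more or less relief? Spending four degrees of freedom on a one-degree question costs power, and this trial has little to spare at 25 per arm.

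At stake is the reading of a null result. This comparison is one of the checks on whether adding the block alters the success of the embolization. A non-significant result from an insensitive test is easily reported as no difference. A chi-square p-value also brings no effect estimate to show what the data can exclude.

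**Working it through.** **1. Inputs from the plan.** There is no stated power or effect for this outcome to reproduce. The arm sizes come from the pain calculation in Section 5: effect size (7 - 5)/2.5 = 0.8 and N = 42. That N is reproduced by a one-sided t-test (21 per arm); a two-sided test needs 26 per arm, or 52, which is a separate matter. Adding 20% gives 42 x 1.2 = 50.4, hence 50, or 25 per arm. If 20% are lost, 25 x 0.8 = 20 per arm. Section 5 also allows an extension to 100 (50 per arm).

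**2. Cell counts, with no assumed distribution.** Two arms by five levels make 10 cells. The mean expected count is 50/10 = 5 with 25 per arm and 40/10 = 4 with 20 per arm. With 25 per arm, some expected count is below 5 unless exactly ten women fall in each level. With 20 per arm it is certain.

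**3. Degrees of freedom.** Put the same noncentrality into 1 or 4 degrees of freedom at two-sided 0.05. Where the 1-df test has 80% power (noncentrality 7.85), the 4-df test has 60%. Likewise 50% becomes 31%, and 30% becomes 18%.

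**4. Simulation (assumptions, not plan figures).** Four reference distributions, best level first, in percent:
- flat: 20/20/20/20/20
- mostly improved: 30/30/25/10/5
- middle: 10/25/35/20/10
- ceiling: 50/25/15/5/5

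The other arm is shifted by a common odds ratio: each cumulative proportion c becomes OR x c / (1 + (OR - 1) x c). For the mostly improved case at OR 3, the first is 3 x 0.30 / (1 + 2 x 0.30) = 0.5625. Each setting has 40,000 trials, analysed by Pearson chi-square (df = non-empty levels minus 1), tie-corrected Wilcoxon, and chi-square on the split at 50% improvement or better.

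Power, mostly improved distribution:

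| Per arm | OR | 2x5 chi-square | Wilcoxon | Ratio | Split at 50% |
|---|---|---|---|---|---|
| 25 | 2 | 13% | 26% | 0.49 | 12% |
| 25 | 3 | 31% | 55% | 0.57 | 19% |
| 25 | 4 | 48% | 73% | 0.65 | 25% |
| 25 | 6 | 71% | 90% | 0.79 | 31% |
| 20 | 2 | 11% | 22% | 0.48 | 9% |
| 20 | 3 | 24% | 45% | 0.53 | 14% |

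Ratio of chi-square to Wilcoxon power over all four distributions:

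| Per arm | OR 2 | OR 3 | OR 4 | OR 6 |
|---|---|---|---|---|
| 20-25 | 0.44-0.55 | 0.47-0.61 | 0.52-0.69 | 0.60-0.83 |
| 50 | 0.54-0.61 | 0.68-0.78 | 0.81-0.91 | 0.93-0.98 |

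**5. Dichotomising.** In the mostly improved and ceiling cases (85% and 90% at 50% improvement or better), the split has less power than the 2x5 table. In the flat and middle cases it does slightly better than the 2x5 table at OR 2-3 but stays below Wilcoxon: at OR 2 with 25 per arm, flat gives 22% (split), 15% (2x5) and 27% (Wilcoxon).

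**6. Type I error.** With no difference and 20-25 per arm, the chi-square rejects in about 3-5% of trials and Wilcoxon in about 5%. This holds although 43-74% of cells on average have an expected count below 5 across the simulated settings.

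**The case against.** - **The plan never assigns a 2x5 chi-square to this item.** True. Success is undefined, its wording suggests a yes/no outcome, and chi-square is standard for a 2x2 table. A reader might infer that the plan commits to the five-level test; it does not. This changes the description more than the remedy. The binary reading is also less powerful than a rank test in every case examined, and it leaves the cut-point open to choice after the data are seen.
- **Other measures cover symptom relief.** Also true. Section 7.8 has the UFS-QoL completed at the first and last consultations, and Appendix V adds a 0-10 satisfaction score and percent necrosis. The check on clinical outcome does not rest on this item alone.
- **No effect is expected.** Section 1.4 gives a 4-8 hour duration for the original block agent and a similar one for its replacement, while this outcome is read at 4-6 months. The odds ratios are illustrations. At OR 2 even Wilcoxon has only about 19-27% power with 20-25 per arm.
- **The simulations favour the rank test.** Proportional odds is the pattern it detects best. In a constructed case, 30/35/20/10/5 against 50/10/10/10/20 with 25 per arm, the chi-square has about 60% power and Wilcoxon about 6-7%. So there is a trade-off, though for a question about more or less relief the ordered alternative is the natural one.
- **Sparse cells do no real harm.** This stands as to false positives. A reader might infer from the small expected counts that the p-values would be invalid, but the test is only mildly conservative.

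**Conclusion.** The point holds as a cheap improvement. The item is ordered, the only named test for categorical data ignores order, and a better-matched analysis is available for the same data.

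It is tempting to say that the plan halves the power. The documents do not support that as a fixed figure. A ratio of about 0.44-0.61 applies to assumed proportional-odds shifts of OR 2-3 with 20-25 per arm. At OR 4-6 the ratio is 0.52-0.83, and with 50 per arm it reaches 0.98 at the largest shift. Nor would the change make this a dependable check: power for modest shifts stays low with either test. The loss is one of sensitivity in one item of one secondary outcome, without excess false positives. The pain and analgesic comparisons are untouched.

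**What to change.** In Section 8, and in the matching synopsis paragraph, state that the five-level clinical-outcome item is compared between arms with a Wilcoxon rank-sum test or a proportional-odds model, reporting the common odds ratio with its 95% CI. Keep chi-square for binary or unordered items, with an exact test when expected counts are small. If a yes/no definition of clinical success is also wanted, fix its cut-point in advance and report it alongside the ordinal result. Add that a non-significant result will be read from the confidence interval and not as evidence of no difference.

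The cost is a sentence or two, with no change to forms, data or patients. The price is lower sensitivity to non-monotone differences; showing the full five-level table by arm lets a reader see such a pattern.
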